| Eligibility criteria Inclusion and exclusion criteria, Informed consent and privacy form | X | | |
| Baseline information (Socio-)demographic variables: age, gender, race, geographic location, housing situation, marital status, educational and employment status | X | | |
| Weight, body mass index | X | X | X |
| Physical examination | X | X | X |
| Life Habits Smoking (yes/no, number of pack/years, smoke duration) | X | X | X |
| Medical History and concomitant diseases. - Charlson Comorbidity Index. | X | X | X |
| COPD medical history: Date of COPD diagnosis (years from diagnosis); n° of COPD exacerbations/year during the previous year to enrolment visit | X | | |
| Functional assessment Lung function test results (FEV1, FVC, FEV1 % of the predicted, RV, TLC,DLCO) according to clinical practice | X | X | X |
| CAT questionnaire | X | X | X |
| COPD Exacerbations** after enrollment Onset and resolution date Severity (mild, moderate, severe) | X | X | X |
| Disease severity (GOLD 2015 Guidelines) | X | X | X |
| Medications related to COPD, COPD exacerbations and adverse events (LABA, LAMA, SABA, SAMA, ICS/LABA, steroids, antibiotics, etc.): drug, dose, frequency, duration of therapy. - Long-Term Oxygen Therapy (liquid and/or concentrate). | X | X | X |
| Change of therapy during observation period and reason for change. | | X | X |
| Non Pharmacological treatment - Pulmonary rehabilitation- | X | X | X |
| Health-care resource consumption related to COPD, COPD | X | X | X |

| Study Visits | Visit 1 | Visit 2 | Visit 3 |
|--|----------|-----------------|-------------------|
| | Baseline | Follow-up | Follow-up 2 |
| Months | 0 | 6 (+/-1) | 12 (+/- 1) |
| exacerbations and adverse events: 
 • Drugs • hospitalization (inward and day hospital) • emergency room access • outpatient visits • GP visits • laboratory tests • clinical examinations | | | |
| Patient Reported Outcomes Questionnaires/scales | | | |
| TSQM-9 | X | X | X |
| MMRC (modified MRC dyspnea scale) | X | X | X |
| CAT | X | X | X |
| MMAS-4 (Morisky Medication-Taking Adherence Scale) | X | X | X |
| Brief Illness Perception Questionnaire | X | X | X |
| Awareness structured interview | X | X | X |
| S(AE) assessment | | X | X |

Table 1. Recorded variables.

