The Morisky medication Adherence Scale 4 items (MMAS-4) is a self-reported, medication-taking behavior scale and consists of four questions about the way patients might experience drug errors or omissions. Each item [F13_MMAS_4.MMAS_4_1 - MMAS_4_4] has a scoring scheme of "Yes" = 0 and "No" = 1. Items are summed to give a non-adherence score ranging from 0 to 4; a higher score means better adherence to therapy (Morisky DE, Green LW, Levine DM. Concurrent and predictive validity of a self-reported measure of medication adherence. *Med Care*. 1986 Jan;24(1):67-74).

The score can be calculated if at least 3 out of 4 of the items are completed. If only one item is omitted, the value for the missing item is the group median of this item that has been completed by all eligible participants. This median value will be imputed for all eligible cases who did not answer this item.

Changes in the MMAS-4 score at each follow-up visit from enrollment will be calculated, for each patient, as the following difference: (score at 6/12 months - score at enrollment), if both scores are available.

COPD pharmacological treatments (classes) ongoing at enrollment

All COPD pharmacological treatments having "End date of therapy" [F20_COPD_PHARMACOLOGICAL_THERAPY.END_DATE_THER] > "Date of enrollment visit" [PatientInfo.Date_enrollment] OR ("End date of therapy" missing and "Ongoing at the end of observation?" [F20_COPD_PHARMACOLOGICAL_THERAPY.ONGOING_THER] = "Yes").

Drug names will be coded by CDM and grouped according to the following categories:

- LAMA alone
- LABA alone

- ICS alone
- LABA + LAMA (Fixed dose combination or not)
- LABA + ICS (Fixed dose combination or not)
- LABA + LAMA + ICS
- SABA or SAMA on demand
- Other: pharmacological therapies for COPD not included in the previous classes.

Categories above are not mutually exclusive: a patient could be classified in more than one category (i.e. if a patient is receiving LABA and SABA on demand, [REDACTED] will be classified both in the “LABA alone” and in the “SABA or SAMA on demand” classes). Only therapies for COPD will be considered (i.e. those records with field Therapy for [F20_COPD PHARMACOLOGICAL THERAPY.THERAPY_FOR] = “COPD”), while therapies for COPD exacerbations or for COPD-related adverse events will not be considered nor classified.

COPD pharmacological treatments (classes) ongoing at 6- and 12-month follow-up visit

At each follow-up visit, all COPD treatments classes (see algorithm above) having

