- (“Start date of therapy” [F20_COPD PHARMACOLOGICAL THERAPY.START_DATE_THER] not missing AND < “Date of follow up visit” [F19_PATIENT_DISPOSITION.PD_2]) AND
- “End date of therapy” [F20_COPD PHARMACOLOGICAL THERAPY.END_DATE_THER] not missing AND > “Date of follow up visit” [F19_PATIENT_DISPOSITION.PD_2]) OR (“End date of therapy” missing AND “Ongoing at the end of observation?” [F20_COPD PHARMACOLOGICAL THERAPY.ONGOING_THER] = “Yes”).

Drug names will be coded by CDM and grouped according to the categories specified above.

Only therapies for COPD will be considered (i.e. those records with field Therapy for [F20_COPD PHARMACOLOGICAL THERAPY.THERAPY_FOR] = “COPD”), while therapies for COPD exacerbations or for COPD-related adverse events will not be considered.

COPD pharmacological treatments: fixed and non-fixed therapy

Patients with fixed COPD pharmacological treatments are those having at least one record of the COPD PHARMACOLOGICAL THERAPY form with “Is it a fixed dose combination?” [F20_COPD PHARMACOLOGICAL THERAPY.DOSE_2] = “Yes” for therapies ongoing at enrollment (see above).

Patients with non-fixed COPD pharmacological treatments are those having at least one record of the COPD PHARMACOLOGICAL THERAPY form with “Is it a fixed dose combination?” [F20_COPD PHARMACOLOGICAL THERAPY.DOSE_2] = “No” for therapies ongoing at enrollment (see above).

Patients who satisfy both conditions will be defined as **patients receiving both COPD pharmacological fixed and non-fixed therapy** at enrollment.

Data manager will check the congruence between the field “Drug” [F20_COPD PHARMACOLOGICAL THERAPY.DRUG] and the question “Is it a fixed dose combination?”: if any fixed dose drug will be entered in the field “Drug” and the question “Is it a fixed dose combination?” = “No” a query will be sent to the investigator. The vice-versa will be checked as well.

Only therapies for COPD will be considered, while therapies for COPD exacerbations or for COPD-related adverse events will not be considered.

COPD pharmacological treatments: patients switching and not switching treatments

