9. Tutto considerato, quanto è soddisfatto/a o insoddisfatto/a del farmaco?

- ₁ Estremamente insoddisfatto/a
- ₂ Molto insoddisfatto/a
- ₃ Insoddisfatto/a
- ₄ Moderatamente soddisfatto/a
- ₅ Soddisfatto/a
- ₆ Molto soddisfatto/a
- ₇ Estremamente soddisfatto/a

- English version

TSQM-9

Abbreviated Treatment Satisfaction Questionnaire for Medication

Instructions: Please take some time to think about your level of satisfaction or dissatisfaction with the medication you are taking in this clinical trial. We are interested in your evaluation of the effectiveness, side effects, and convenience of the medication *over the last two to three weeks, or since you last used it*. For each question, please place a single check mark next to the response that most closely corresponds to your own experiences.

1. How satisfied or dissatisfied are you with the ability of the medication to prevent or treat your condition?

- ₁ Extremely Dissatisfied
- ₂ Very Dissatisfied
- ₃ Dissatisfied
- ₄ Somewhat Satisfied
- ₅ Satisfied
- ₆ Very Satisfied
- ₇ Extremely Satisfied

2. How satisfied or dissatisfied are you with the way the medication relieves your symptoms?

- ₁ Extremely Dissatisfied
- ₂ Very Dissatisfied
- ₃ Dissatisfied
- ₄ Somewhat Satisfied
- ₅ Satisfied
- ₆ Very Satisfied
- ₇ Extremely Satisfied

3. How satisfied or dissatisfied are you with the amount of time it takes the medication to start working?

- ₁ Extremely Dissatisfied
- ₂ Very Dissatisfied
- ₃ Dissatisfied
- ₄ Somewhat Satisfied
- ₅ Satisfied
- ₆ Very Satisfied
- ₇ Extremely Satisfied

4. How easy or difficult is it to use the medication in its current form?

- ₁ Extremely Difficult
- ₂ Very Difficult
- ₃ Difficult
- ₄ Somewhat Easy
- ₅ Easy
- ₆ Very Easy
- ₇ Extremely Easy

5. How easy or difficult is it to plan when you will use the medication each time?

- ₁ Extremely Difficult
- ₂ Very Difficult
- ₃ Difficult
- ₄ Somewhat Easy
- ₅ Easy
- ₆ Very Easy
- ₇ Extremely Easy

6. How convenient or inconvenient is it to take the medication as instructed?

- ₁ Extremely Inconvenient
- ₂ Very Inconvenient
- ₃ Inconvenient
- ₄ Somewhat Convenient
- ₅ Convenient
- ₆ Very Convenient
- ₇ Extremely Convenient

7. Overall, how confident are you that taking this medication is a good thing for you?

- ₁ Not at All Confident
- ₂ A Little Confident
- ₃ Somewhat Confident
- ₄ Very Confident
- ₅ Extremely Confident

8. How certain are you that the good things about your medication outweigh the bad things?

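### The SAP rule for COPD drugs ongoing at a follow-up visit mishandles changes made on the visit day, and its unbalanced bracket allows two readings, each of which can misstate Tables 34 and 35

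*SAP*

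**What the plan says.** SAP section 3 (Computed variables) gives the rule for treatment classes ongoing at the 6- and 12-month visits in two bullets.

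- The start date must be present and strictly earlier than the visit: "not missing AND < “Date of follow up visit” [F19_PATIENT_DISPOSITION.PD_2]) AND".
- The end date must be present and strictly later than the visit: "F20_COPD PHARMACOLOGICAL THERAPY.END_DATE_THER] not missing AND > “Date of follow up visit” [F19_PATIENT_DISPOSITION.PD_2]) OR". The OR leads to an alternative for drugs with no end date that are flagged as ongoing: "OR (“End date of therapy” missing AND “Ongoing at the end of observation".

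The second bullet has a closing parenthesis after the visit-date field with no matching opening one. Nothing is said about a start or end date that equals the visit date.

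On classes, the same section says: "Categories above are not mutually exclusive: a patient could be classified in more than one category". SAP section 4.10 reports the classes at 6 and 12 months in Tables 34 and 35, as percentages of all FAS patients.

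Two other rules in SAP section 3 follow different conventions. The enrollment rule behind Table 33 has a strict end-date test but no start-date condition. The oxygen-therapy rule uses an inclusive sign on the start date.

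**The concern.** The study visits follow routine clinic practice, and Protocol Table 1 records at visits 2 and 3 the item "Change of therapy during observation period and reason for change". A prescription change on the visit day is therefore foreseeable, and it is the case that the two strict signs leave out. If the old record closes and the new one opens on the visit date, the first fails the end-date test and the second can fail the start-date test.

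What is at stake is the description of treatment over time. Protocol section 9.7 plans to describe changes in COPD medication since baseline, and the rule loses information for patients who had a change. Because the denominator is the whole FAS, a patient who drops out of every class still counts below the line. That patient cannot be told apart from an FAS patient who had no such visit.

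The planned checks are unlikely to reveal this. SAP section 6 lists Table 33, but not Tables 34 or 35, for reprogramming or independent verification. Its checks of derived variables test agreement with the SAP algorithm, so they would confirm the rule as written.

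**Working it through.** The plan gives no figure here to reproduce, so the check is to apply the rule to test records around a visit on day V.

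**Inputs.** The start-date test, end-date test and no-end-date branch come from SAP section 3. The denominator of Tables 34 and 35 comes from SAP section 4.10. The range of 320 to 380 evaluable patients comes from Protocol section 9.5.

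**Rules compared.**

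- Reading A (each bullet is a condition): start < V AND (end > V OR (end missing AND ongoing flag = Yes)).
- Reading B (as typed, AND before OR): (start < V AND end > V) OR (end missing AND ongoing flag = Yes).
- Proposed rule: start < V AND (end >= V OR (end missing AND ongoing flag = Yes)).

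**Results with V = day 180.**

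| Record | A | B | Proposed |
|---|---|---|---|
| Old drug, ended on V | out | out | in |
| Old drug, ended on V - 1 | out | out | out |
| Old drug, ended on V + 1 | in | in | in |
| New drug, started on V, ongoing at the end | out | in | out |
| New drug, started on V, stopped on day 300 | out | out | out |
| Drug started on V + 90, ongoing at the end | out | in | out |
| Unchanged co-medication | in | in | in |

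**What follows.**

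1. Under A, a visit-day change always loses both the old and the new drug.
2. Under B, the old drug is always lost. The new drug is lost only if it was itself stopped later.
3. Under B there is an opposite fault: the start-date test no longer applies to ongoing drugs. A drug begun 90 days after the 6-month visit and never stopped is counted as in use at 6 months.
4. A patient falls into no class only if no other COPD drug continued across the visit. Otherwise the class may be wrong. For example, take a patient on separate LABA and LAMA products whose LAMA is replaced by another LAMA on the visit day. Under A only the LABA is left, so the patient is counted under LABA alone instead of the combination.

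**Size per patient.** One patient is 100/380 = 0.26 percentage points, or 100/320 = 0.31. A misclassified patient moves two percentages, one down and one up.

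**Number of patients.** The documents give no rate, so these shares are assumptions:

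| Assumed share changed on the visit day | N = 320 | N = 380 |
|---|---|---|
| 1% | 3.2 | 3.8 |
| 5% | 16 | 19 |
| 10% | 32 | 38 |

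**The case against.** The strongest reply is that this is a tie-handling gap in two descriptive tables, and that more can easily be read into it than the documents support. Four stronger inferences are tempting.

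- **That every visit-day change loses both drugs.** This holds on reading A, which the bullets suggest. On reading B a replacement that continues to the end of observation is kept. The bracket does not rescue the rule, because reading B loses the old drug and admits drugs started after the visit.
- **That these patients appear untreated.** This needs the whole COPD regimen to change that day, and the description of Tables 34 and 35 has no untreated row. The supported statement is no class or the wrong class.
- **That treatment looks more stable than it was.** This cannot be derived. The tables are cross-sectional, and losing changers could equally look like a fall in use after enrollment. Switching has its own definition, which does not use these visit-date tests.
- **That satisfaction results are affected.** The TSQM-9 asks about experience "over the last two to three weeks, or since you last used it", so the drug in use before the visit is the one being rated. But no planned TSQM-9 summary, regression, correlation or switcher comparison uses this rule, and Protocol section 9.7 pools all treatments.

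Two further objections stand in part. The size depends on investigators entering the visit date as both end and start date, and the eCRF conventions are not in the documents. This is least certain at 12 months, where a prescription issued as follow-up closes may not get a new record. Also, an inclusive end date at follow-up alone would differ from the strict one at enrollment, so the fix has to cover both.

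**Conclusion.** The concern holds in a limited form. The SAP rule can give a wrong classification on either reading of its brackets, so this is more than missing detail. On the bulleted reading it drops both drugs at a visit-day change. On the other it drops the stopped drug and can count one not yet started.

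The effect is confined to the numerators of Tables 34 and 35, at about 0.26 to 0.31 percentage points per affected patient. Those figures assume an FAS between 320 and 380. The total cannot be stated, because neither the rate of visit-day changes nor the date-entry convention is documented. At an assumed 1% it is 3 to 4 patients per visit, which is negligible; at an assumed 10% it is 32 to 38, which would visibly alter the class distribution. The primary analysis and the model-based results are untouched.

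**What to change.** In SAP section 3, define a treatment as ongoing at a follow-up visit by:

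start date < visit date AND (end date >= visit date OR (end date missing AND ongoing flag = Yes))

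with all brackets closed. This assigns the drug in use up to the visit.

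Only one side should be inclusive. If both are, the old and the new drug are counted together and a replacement can show up as a false combination class. Making the start date inclusive and keeping the end date strict would also resolve the tie, assigning the new drug instead. The version above is preferred because it matches the period that the TSQM-9 asks about.

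Apply the same end-date convention to the enrollment rule so that Tables 33 to 35 can be compared. That rule also lacks a start-date condition, so full comparability needs one there too. The eligibility derivation for criterion 4 in SAP section 2.1 uses a strict end date as well. It serves a different purpose, but the SAP should say that the difference is intended.

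The cost is one comparison sign and the brackets, plus the matching edit at enrollment; no new data are needed. The small downside is that a drug stopped on the visit day is shown as in use at that visit, which a table footnote can state.

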Non-parametric bootstrap method will be applied to cost data for calculating 95% confidence intervals (22-23).

A multiple linear regression model will be performed to investigate statistical significance of INHS cost predictors (24).

#4 To assess the correlation between patients' satisfaction and resource utilization.

Correlation indexes will be calculated between treatment satisfaction domain scores of TSQM-9 and healthcare resource consumption (such as number of hospitalizations, emergency room accesses, GP visits, laboratory test. etc... during observation period) at 12-month follow-up visit. The patients switching treatment during observation period will not be excluded from analysis and will be evaluated at each visit. The patients stopping treatment during study will be censored at their last available visit.

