- Inclusion criterion "4. Patients requiring regular treatment according to GOLD guidelines, i.e.: undergoing stable pharmacological treatment for COPD since at least 3 months" not checked in the PROTOCOL DEVIATION FORM [\[F24_PROTOCOL_DEVIATION_FORM.PD_CI_4\]](#) AND
- COPD Pharmacological therapy form: Start date of therapy (dd/mmm/yyyy) not missing AND (Start date of therapy (dd/mmm/yyyy) [\[F20_COPD_PHARMACOLOGICAL_THERAPY.START_DATE_THER\]](#) < Date of enrolment visit (dd/mm/yyyy) - 3*30.4375 [\[_PatientInfo.Date_enrollment\]](#) OR Start date of therapy (dd/mmm/yyyy) > Date of enrolment visit (dd/mm/yyyy)) AND
- COPD Pharmacological therapy form: End date of therapy (dd/mmm/yyyy) [\[F20_COPD_PHARMACOLOGICAL_THERAPY.END_DATE_THER\]](#) = missing OR End date of therapy (dd/mmm/yyyy) > Date of enrolment visit (dd/mm/yyyy) [\[_PatientInfo.Date_enrollment\]](#)

Criterion 5: Written informed consent to both participation in the study and privacy form

- Question "5. Is a written informed consent to both participation in the study and privacy form available?" = "Yes" [\[F01_INC_EXC_CRITERIA.CI_5\]](#) AND
- Inclusion criterion "5. Written informed consent to both participation in the study and privacy form" not checked in the PROTOCOL DEVIATION FORM [\[F24_PROTOCOL_DEVIATION_FORM.PD_CI_5\]](#) AND
- Date of informed consent signature (dd/mm/yyyy) not missing [\[_PatientInfo.Date_CI\]](#) AND
- Date of privacy form signature (dd/mm/yyyy) not missing [\[_PatientInfo.Date_privacy\]](#) AND
- Date of informed consent signature (dd/mm/yyyy) = Date of privacy form signature (dd/mm/yyyy) AND
- Date of informed consent signature (dd/mm/yyyy) ≤ Date of enrolment visit (dd/mm/yyyy)

Criterion 6: Patients capable of discernment and able to read or write in Italian language

- Question "6. Is the patient capable of discernment and able to read or write in Italian language?" = "Yes" [\[F01_INC_EXC_CRITERIA.CI_6\]](#) AND
- Inclusion criterion "6. Patients capable of discernment and able to read or write in Italian language" not checked in the PROTOCOL DEVIATION FORM [\[F24_PROTOCOL_DEVIATION_FORM.PD_IC_6\]](#)

Exclusion criteria**Criterion 7: Patients who are currently participating in a clinical trial on experimental drugs**

- Question "7. Does the patient currently participate in a clinical trial on experimental drugs?" = "No" [\[F01_INC_EXC_CRITERIA.EC_1\]](#) AND

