Considering only COPD pharmacological treatments (i.e. those records with field “Therapy for” [F20_COPD PHARMACOLOGICAL THERAPY.THERAPY_FOR] = “COPD”) ongoing at enrollment or started after enrollment (i.e. with “Ongoing at the end of observation?” [F20_COPD PHARMACOLOGICAL THERAPY.ONGOING_THER] = “Yes” OR with “Start date of therapy” [F20_COPD PHARMACOLOGICAL THERAPY.START_DATE_THER] > “Enrollment date”), patients who switched treatment during the observation period* will be those with more than one record with the above-mentioned characteristics in the COPD PHARMACOLOGICAL THERAPY log form, excluding therapies started the very same day according to Start date of therapy. In particular, patients switching treatment are those with at least one change in the drug/frequency/route/formulation/device of administration after enrollment (also adding / stopping a COPD treatment is a switch).

*switches occurred before enrollment will not be considered.

Number of therapies administered for COPD, COPD-related adverse events and COPD exacerbations

The **number of therapies administered for COPD per patient during observation period** will be calculated as the sum of records of the COPD PHARMACOLOGICAL THERAPY log form considering only pharmacological treatments for COPD (i.e. those records with field "Therapy for" [F20_COPD PHARMACOLOGICAL THERAPY. THERAPY_FOR] = "COPD") ongoing at enrollment or started after enrollment (i.e. with "Ongoing at the end of observation?" [F20_COPD PHARMACOLOGICAL THERAPY. ONGOING_THER] = "Yes" OR with "Start date of therapy" [F20_COPD PHARMACOLOGICAL THERAPY. START_DATE_THER] > "Enrollment date").

Similarly, the **number of therapies administered for COPD-related adverse events and COPD exacerbations per patient during observation period** will be calculated as the sum of records of the COPD PHARMACOLOGICAL THERAPY log form considering only pharmacological treatments for COPD-related adverse events and COPD exacerbations (i.e. those records with field "Therapy for" [F20_COPD PHARMACOLOGICAL THERAPY. THERAPY_FOR] = "COPD-related adverse event" OR "COPD exacerbation") ongoing at enrollment or started after enrollment (i.e. with "Ongoing at the end of observation?" [F20_COPD PHARMACOLOGICAL THERAPY. ONGOING_THER] = "Yes" OR with "Start date of therapy" [F20_COPD PHARMACOLOGICAL THERAPY. START_DATE_THER] > "Enrollment date").

Exacerbations during the observation period

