The table will provide the distribution of patients according to the field "Therapy for the event" [[F22_AES_AND_ADRS.AE_THERAPY](#)] (i.e. patients who received medications for adverse events during the study).

Percentages will be computed out of the total number of patients evaluable for the FAS.

4.11 Correlation between patients' satisfaction and resource utilization (secondary objective #4)

Table 37. Correlation between patients' satisfaction and resource utilization (including drugs)

A correlation index (Pearson or Spearman) will be computed between TSQM-9 subscales scores (as defined in "Computed variables" chapter) at 12 month follow-up visit and the number of hospitalizations per patient during observation period (as defined in "Computed variables" chapter); p-value will be provided as well.

A correlation index (Pearson or Spearman) will be computed between TSQM-9 subscales scores (as defined in "Computed variables" chapter) at 12 month follow-up visit and the number of ER accesses per patient during observation period (as defined in "Computed variables" chapter); p-value will be provided as well.

A correlation index (Pearson or Spearman) will be computed between TSQM-9 subscales scores (as defined in "Computed variables" chapter) at 12 month follow-up visit and the number of specialist visits per patient during observation period (as defined in "Computed variables" chapter); p-value will be provided as well.

A correlation index (Pearson or Spearman) will be computed between TSQM-9 subscales scores (as defined in "Computed variables" chapter) at 12 month follow-up visit and the number of general practitioner visits per patient during observation period (as defined in "Computed variables" chapter); p-value will be provided as well.

A correlation index (Pearson or Spearman) will be computed between TSQM-9 subscales scores (as defined in "Computed variables" chapter) at 12 month follow-up visit and the number of laboratory test per patient during observation period (as defined in "Computed variables" chapter); p-value will be provided as well.

A correlation index (Pearson or Spearman) will be computed between TSQM-9 subscales scores (as defined in "Computed variables" chapter) at 12 month follow-up visit and the number of therapies administered for COPD per patient during observation period (as defined in "Computed variables" chapter); p-value will be provided as well.

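### SAP 3 codes COPD drugs ongoing at enrolment by their status at the end of observation, so drugs stopped or replaced in follow-up drop out of the Table 37 therapy count and some switchers are missed

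*SAP*

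**What the plan says.** SAP section 3 (Computed variables) defines two things from the COPD pharmacological therapy log with one filter: who switched treatment, and how many therapies each patient received. The filter is worded as "ongoing at enrollment or started after enrollment (i.e. with “Ongoing at the end of observation" answered Yes, or a start date after enrolment. It has no end-date condition. It appears three times: in the switcher rule, in the COPD therapy count, and in the count of therapies for COPD-related adverse events and exacerbations.

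For switching, the section first gives a counting rule: "patients who switched treatment during the observation period* will be those with more than one record with the above-mentioned characteristics", leaving out therapies that start on the same day. The next sentence defines switchers by "at least one change in the drug/frequency/route/formulation/device of administration after enrollment (also adding / stopping a COPD treatment is a switch"). A footnote to the counting rule adds that "switches occurred before enrollment will not be considered", without any field coding.

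The therapy count goes into SAP 4.11, Table 37, where TSQM-9 subscale scores at 12 months are correlated with "the number of therapies administered for COPD per patient during observation period", with a p-value. For this objective Protocol 9.7 states: "The patients switching treatment during observation period will not be excluded from analysis and will be evaluated at each visit".

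**The concern.** Being on a drug at enrolment and being on it at the end of observation are different facts. They differ exactly for patients whose enrolment treatment changed. The filter therefore loses records selectively: a drug started before enrolment and ended in follow-up is dropped, while a drug started after enrolment is kept even if it is later stopped.

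Two results are at stake.

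- **Table 37.** The COPD therapy count contradicts its own worded definition. A one-for-one replacement leaves no trace in the correlation with satisfaction.
- **Switcher flag.** One paragraph holds two rules that classify the same patient differently. The titles of Tables 45 and 46, and the Table 45 quality check in SAP section 6, indicate that those tables use this flag. Their own text is not visible.

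The oxygen flag in SAP section 3 has a similar gap. It requires a start on or after enrolment, or therapy ongoing at the end of observation, so it misses patients on oxygen at enrolment who later stopped.

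**Working it through.** The plan gives no figure to reproduce here, so this is a check of derivation logic.

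**1. The definitions side by side**

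- Switcher and therapy-count filter (SAP 3): ongoing at end of observation = Yes, OR start > enrolment.
- Treatment classes ongoing at enrolment (SAP 3): end > enrolment, OR end missing with ongoing = Yes.
- Full analysis set, criterion 4 (SAP 2.1): start more than 3 × 30.4375 = 91.3 days before enrolment, or after enrolment; and end date "missing OR End date of therapy (dd/mmm/yyyy) > Date of enrolment visit (dd/mm/yyyy").

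Take a drug that starts 400 days before enrolment and ends on day 180. It passes criterion 4, so it can occur in the full analysis set. It counts as ongoing at enrolment under the treatment-class definition. Under the filter it fails both conditions: it is not ongoing at the end, and it did not start after enrolment.

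**2. Consequence for each patient**

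Coded count = worded count − number of enrolment drugs ended in follow-up. A and B are enrolment drugs unless stated otherwise.

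| History | Worded count | Coded count | Record-count rule | Narrative sentence |
|---|---|---|---|---|
| A unchanged | 1 | 1 | no switch | no switch |
| A replaced once by B | 2 | 1 | no switch | switch |
| A stopped, nothing after | 1 | 0 | no switch | switch |
| A and B, B stopped | 2 | 1 | no switch | switch |
| A and B, both replaced by C | 3 | 1 | no switch | switch |
| A replaced by B and C on one day | 3 | 2 | no switch | switch |
| A and B, B replaced by C | 3 | 2 | switch | switch |
| A to B to C | 3 | 2 | switch | switch |
| A kept, B added | 2 | 2 | switch | switch |
| A and B unchanged, different start dates | 2 | 2 | switch, unless the footnote is coded | no switch |

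**3. Wider logic check**

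The histories are: one or two enrolment drugs; each kept, stopped or replaced once; two-drug patients with the same or different start dates; with or without one add-on. That gives 3 × 2 = 6 one-drug and 2 × 3 × 3 × 2 = 36 two-drug histories, 42 in all.

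- The coded count is below the worded count in 2 × 2 = 4 one-drug and 2 × 8 × 2 = 32 two-drug histories, so 36 of 42. This is every history in which an enrolment drug ends.
- With the footnote applied and all changes on different days, the record-count rule misses 3 one-drug and 6 + 6 two-drug switchers, 15 in total, with no false flags.
- Without the footnote there is one further disagreement, a false flag: two unchanged drugs with different start dates. The total is then 16.
- If both replacements fall on one day, the missed switchers rise from 15 to 17.

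These are counts of constructed histories and say nothing about patient rates.

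**4. Would the planned checks find it?**

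In SAP section 6, the Table 37 check covers correlation coefficients and p-values, not the therapy counts. The Table 45 check reviews switcher status in 50% of evaluable patients but does not say which of the two rules is the reference.

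**The case against.** The mismatch between words and coding is not in dispute. The arguments against giving it weight are these.

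- **The count may not measure what the correction assumes.** The SAP counts log records and treats a change of frequency or device as a switch. If such a change opens a new record for the same drug, the corrected count gives two therapies for one drug. This is fair, but counting records is the SAP's own definition. It is a reason to state how same-drug records are handled, not to keep the present coding. Nor is it shown which way any correlation would move.
- **The narrative sentence captures every missed switcher.** True, if that sentence is what gets programmed. The text does not say which rule governs.
- **The grid adds little.** The 36 of 42 follows by construction, and 14 of the 15 missed switchers involve a stopped drug. Only one is a pure replacement. The grid shows where the rules diverge, not how often.
- **The reach is small.** The COPD therapy count is one of seven resource variables in Table 37, so 3 of 7 × 3 = 21 correlations. Protocol 9.7 expects few patients to stop treatment and censors them, so the case of a sole drug stopped may rarely enter. The adverse-event and exacerbation count is affected only where such a therapy was already ongoing at enrolment. Table 31 lists oxygen records with dates. All of this stands, and it limits the severity.
- **Undated stops remain.** An enrolment drug that stopped with no recorded end date would still be dropped by an end-date rule. This is a residual gap shared with the SAP's own treatment-class definition.

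**Conclusion.** The point holds and should be fixed, though it does not touch the primary analysis. Followed as written, the Table 37 COPD therapy count is too low by one for each enrolment drug ended in follow-up, and the record-count rule misses some, not all, of the switchers that the adjoining sentence includes. Patients with a replaced drug do enter Table 37: the protocol keeps switchers, and Chart 1 in SAP 2.3 assigns this analysis to patients evaluable at 12 months.

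The number of patients affected is unknown, because neither document gives a switching rate. The conclusion assumes that the field conditions are programmed as stated. The grid counts also assume that changes fall on different days. The false flag for two unchanged drugs arises only if the footnote is left out of the program. For Tables 45 and 46 the effect is inferred from their titles and the quality-check text. TSQM-9 Tables 10 and 11 and the regression models in Tables 17 to 19 do not use these variables.

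**What to change.** **Record selection.** Keep a COPD record if:

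- (a) it starts after enrolment, whatever its end date or ongoing status, so that post-enrolment starts with status not known or not available are retained; or
- (b) it starts on or before enrolment and its end date is after enrolment, or is missing with ongoing = Yes.

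Use this selection for both Table 37 therapy counts. State whether a regimen change that opens a new record for the same drug counts as a further therapy. Query enrolment drugs that have neither an end date nor an ongoing status of Yes.

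**Switcher flag.** Replace the record count with the narrative rule: at least one dated change, addition or stop after enrolment. Same-day starts count as one event and do not cancel the flag. Code the footnote explicitly, so that only events dated after enrolment count. The change-of-therapy item collected at Visits 2 and 3 (Protocol Table 1) can serve as a cross-check.

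**Oxygen flag.** Add records that began before enrolment and ended after it.

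**Quality checks.** Name the new switcher rule as the reference for the Table 45 check, and add the therapy counts to the Table 37 check.

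**Cost.** SAP rewording and reprogramming of the therapy counts, the switcher flag and the oxygen flag. Start dates, end dates and ongoing status are already in the log forms, so no new data collection is needed.
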